5.2 Treatment Regimen

Based upon our previous experience with Definity and according to the manufacturer's instruction in the package insert, two vials of Definity will be mixed and diluted in 50 ml of normal saline, yielding a concentration of 49.4 µl/ml. For the purpose of contrast-enhanced imaging, Definity will be infused over

approximately 10-12 minutes, during which time pulse inversion HI and SHI will be performed.

5.3 Risks

The risk of this procedure is basically the risk of an adverse reaction to Definity, and the risks of conventional prostate biopsy. The largest safety studies published to date on the use of ultrasound contrast agents in humans (involving up to 4,300,966 subjects) concluded that these agents have a good safety profile in both cardiac and non-cardiac applications.^{77,78,79,80} In our experience, adverse reactions to Definity include only minor sensations of discomfort which resolve as soon as the infusion is stopped.

5.4 Method for Assigning Subjects to Treatment Groups

n/a, as all subjects will be studied with HI and SHI.

6.0 STUDY PROCEDURES

6.1 Study Visit Schedule

The CEUS study procedure will be performed during a single episode of care at which time the patient will undergo a clinically indicated biopsy of the prostate. No additional visits will be required to participate in the study.

All ultrasound imaging will be performed with a commercially available Logiq E9 ultrasound system that provides conventional color and power Doppler imaging, and which will be modified to provide contrast-enhanced HI and SHI. Because of the very low SHI signal obtained from tissue, SHI is performed with a dual imaging technique that displays a conventional grayscale image alongside the SHI image. The conventional grayscale image is necessary to define the tissue anatomy and determine location within the prostate while the SHI is used to demonstrate vascularity and neovessels.

The proposed microbubble contrast agent for the current study, Definity®, (Perflutren Lipid Microsphere, Lantheus), is a microbubble contrast agent that demonstrates enhancement of the prostate on both grayscale and Doppler imaging. Definity remains stable within the circulation for 3 to 6 minutes after infusion and all contrast-enhanced procedures will need to be completed during the infusion time. This time constraint has not been a problem in prior studies. Based on our previous experience with Definity (and in accordance with the manufacturer's instructions), two vials will be mixed and diluted in 50 ml of

normal saline, yielding a concentration of 49.4 $\mu\text{l/ml}$. A 20 gauge intravenous catheter will be inserted into an arm vein for administration of contrast material. Definity will be delivered as an infusion at an initial rate of 4 ml/min. The infusion rate will be titrated to achieve adequate enhancement of the prostatic microvasculature. Post contrast imaging will begin as soon as contrast is visible. The infusion of Definity will continue for approximately 10-12 minutes during which time the contrast-enhanced diagnostic ultrasound, the assignment of rating scores, and the SHI guided biopsy procedure will be performed.

[figure not shown]
Study participants will be prepared for biopsy according to standard clinical operating procedure for subjects undergoing TRUS-guided biopsy at the Jefferson Prostate Diagnostic Center. Study subjects will be imaged in the lithotomy position with grayscale ultrasound performed to measure gland size.⁸¹ Next, the prostate will be evaluated with both baseline and contrast-enhanced imaging modes. The dynamic range and imaging frequencies for grayscale, and color Doppler imaging will be standardized for all subjects (scanning frequency of 7.0 MHz with dynamic range of 65 dB). The Doppler window for color imaging will include the entire gland. The baseline examination (~5 minutes) will consist of conventional grayscale imaging and color Doppler imaging. Contrast-enhanced imaging (~5-7 minutes) will consist of color Doppler imaging, HI and SHI. In order to allow comparison of the various imaging modes, a standard imaging sweep through the prostate will be performed in the axial plane from the base of the gland to the apex for each of the 2 baseline imaging modes and 3 contrast-enhanced imaging modes.

Study participants will be monitored for AEs during and 30 minutes after contrast administration.

6.2 Study Interpretation

The peripheral zone of each prostate will be rated for suspicion of PCa at 12 sites, including medial and lateral component of each sextant. A 5-point rating score will be assessed in real-time by the examining physician for each ultrasound technique. These scores have been previously described and validated,⁸² with proven utility for predicting the risk of malignancy in prior studies.[Error! Bookmark not defined.](#)[Error! Bookmark not defined.](#) A maximum of 6 sites will be identified as the most suspicious areas on SHI; targeted biopsy specimens will be obtained from these sites under ultrasound guidance during contrast-enhanced imaging. If fewer sites are identified, fewer targeted biopsy cores may be obtained.

The interpretation of CEUS studies will follow a 12 part extended sextant grid as demonstrated in the illustration below:

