1.5 Clinical Data - Prostate

Two basic ultrasound technologies have been used to image microbubble contrast agents in the prostate: Doppler and grayscale HI. These technologies are summarized in a textbook by one of the PIs.⁵² Color and power Doppler imaging techniques, available on most modern ultrasound systems, utilize relatively high energy levels that destroy a large proportion of the microbubbles as they are imaged. Pulse inversion and grayscale HI are technological advances that together permit high resolution, low energy grayscale imaging of contrast agents.^{53,54,55,56} Various pulsing sequences can further improve grayscale HI of the prostatic microcirculation.^{57,58} Flash replenishment imaging was first described as a grayscale harmonic technique that can demonstrate tissue perfusion and may be used for blood flow estimation.^{59,60,61} Contrast-Enhanced Flash Replenishment may be combined with Maximum Intensity Projection (CE-FR-MIP) of each pixel in the image over 2-4 seconds of low power image frames to demonstrate microvascular patterns associated with neovascularity⁶² and PCa.⁶³ Whereas assessment for neovascularity with contrast-enhanced Doppler imaging is based upon the magnitude of contrast enhancement, CE-FR-MIP provides additional information based upon changes to the normal intraprostatic microvascular architecture (Fig. 4).

[figure not shown]

Figure 4. Gleason 7 PCa in the right mid-gland is invisible on grayscale (left image), but tumor vascularity is clearly defined with CE-FR-MIP imaging (right image; arrows).

Numerous trials of CE-TRUS using HI to detect PCa have been conducted at the Jefferson Prostate Diagnostic Center.^{64,65} An early study ($n=100$ subjects) demonstrated improved sensitivity for PCa detection from 38% at baseline to

65% after infusion of the microbubble agent Definity (Lantheus Medical Imaging, N Billerica, MA); $p \leq 0.004$.⁶⁶ Furthermore, lesions detected by contrast-enhancement were generally larger and with a higher Gleason score – that is, they were the more clinically significant cancers. The last 40 subjects in this study were evaluated with targeted biopsy. A suspicious site identified by CE-TRUS was 3.5 times more likely to have a positive biopsy than an adjacent site without contrast enhancement ($p < 0.025$).⁶⁷

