A Department of Defense funded clinical trial of 301 men demonstrated that targeted cores based upon CE-TRUS were twice as likely to return a positive biopsy as systematic cores.⁶⁸ Using CE-FR-MIP, our group demonstrated positive biopsies in 29/225 targeted cores as compared with 50/600 systematic cores, yielding an odds ratio of 2.0 for cancer detection with CE-TRUS ($p = 0.034$).⁶⁹ A recently completed National Cancer Institute (NCI) funded clinical trial ($n = 272$) confirmed increased PCa detection with CE-TRUS, and specifically with CE-FR-MIP (OR=2.1, $p < 0.001$). More significantly, CE-TRUS preferentially detected lesions with greater tumor volume and Gleason score ≥ 7 ($p < 0.001$). ROC analysis for detection of high volume / high grade PCa with CE-TRUS yielded an area under the curve of 0.90 ($p = 0.001$).⁷⁰ Comparison of CE-TRUS HI with whole mount prostatectomy specimens in our DOD and NCI study subjects demonstrated microbubble enhancement in 93% of malignant foci. In summary, PCa's visualized with CE-TRUS tend to be larger and of higher grade.

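### SHI is scored live by the examiner who also scores HI and contrast Doppler, with no fixed order and no locking of scores, so the primary SHI accuracy can absorb what the other contrast modes showed

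*Combined protocol and SAP*

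**What the plan says.** Section 6.2 has 12 peripheral-zone sites rated for suspicion of cancer in each patient: "A 5-point rating score will be assessed in real-time by the examining physician for each ultrasound technique". The sites judged most suspicious on SHI, up to six, then receive targeted cores.

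Section 6.1 describes the session. First: "The baseline examination (~5 minutes) will consist of conventional grayscale imaging and color Doppler imaging". Then: "Contrast-enhanced imaging (~5-7 minutes) will consist of color Doppler imaging, HI and SHI". The sweeps are made alike for a stated purpose: "In order to allow comparison of the various imaging modes, a standard imaging sweep through the prostate will be performed", and this is done "for each of the 2 baseline imaging modes and 3 contrast-enhanced imaging modes". The infusion lasts about 10-12 minutes, during which "the contrast-enhanced diagnostic ultrasound, the assignment of rating scores, and the SHI guided biopsy procedure will be performed". Section 6.1 also explains that SHI is always shown beside a conventional grayscale image.

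Section 3.2 makes sensitivity and specificity of subharmonic CE-TRUS for high-risk, aggressive cancer primary endpoint b. Section 7.2 limits the analysis to rough estimates of these two quantities, if there are enough high-grade cases.

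No section gives an order for the contrast modes, a point at which a mode's scores become final, a separate reader, or a later reading from stored images. The study biopsy comes after the scores, so its result cannot influence them.

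**The concern.** The trial asks what SHI itself shows. If HI or contrast Doppler has already drawn the examiner's eye to a site, a high SHI score at that site may record the earlier impression, not the SHI image. The plan lets this happen and leaves no way to tell afterwards whether it did.

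Three things depend on the SHI reading: primary endpoint b, the choice of sites for targeted cores, and any later use of the parallel sweeps to set SHI against HI. The Study Summary gives improvement of CEUS by subharmonic imaging as the trial's goal, and section 7.1 says that the data are meant for a future grant submission. An accuracy figure partly borrowed from HI would pass into that application as if it belonged to SHI.

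**Working it through.** **1. The plan's own figures.** Inputs from section 7.1: n = 50, high-grade prevalence 15%. Expected cases: 50 × 0.15 = 7.5. Exact binomial: P(X ≥ 5) = 0.888 (plan: 88%), P(X ≤ 3) = 0.046 (plan: 4.6%), P(X = 0) = 0.85^50 = 0.0003 (plan: 0.03%). These reproduce to within rounding and do not depend on how images are read.

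**2. What one patient is worth.** If one high-grade patient is called positive on SHI only because another mode pointed to the site, sensitivity moves by 1/7.5 = 13.3 points (1/8 = 12.5; 1/7 = 14.3). For example, 6/8 = 75% (exact 95% CI 35% to 97%) becomes 7/8 = 87.5% (47% to 100%). The interval describes sampling error only. It would not reveal the borrowed case.

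**3. Sensitivity and specificity under assumed borrowing.** The documents give no SHI accuracy and no borrowing rate, so the inputs here are assumptions.

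- Sensitivity: observed = s + (1 − s)b, where s is the sensitivity of SHI alone and b the share of its misses rescued by other modes. With s from 0.50 to 0.80 and b from 0.10 to 0.50, the smallest rise is 0.80 + 0.20 × 0.10 = 0.82 (2 points) and the largest is 0.50 + 0.50 × 0.50 = 0.75 (25 points).
- Specificity: if the other modes turn a share c of SHI true negatives positive, observed = sp(1 − c). With sp from 0.60 to 0.80 and c from 0.10 to 0.50, the fall runs from 0.60 × 0.10 = 6 points to 0.80 × 0.50 = 40 points. But a clean HI image could equally persuade the examiner to drop an SHI false positive, which raises specificity. The direction is open.

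**4. An AUC illustration and its limits.** Take binormal scores with d = √2·Φ⁻¹(AUC). Let the reader give weight w to HI, with within-class correlation ρ between modes. The apparent AUC is Φ{[(1−w)d_SHI + w·d_HI] / √(2[(1−w)² + w² + 2w(1−w)ρ])}. For HI, use the figure in section 1.5: "ROC analysis for detection of high volume / high grade PCa with CE-TRUS yielded an area under the curve of 0.90". That figure is for CE-TRUS in a narrower disease category than endpoint b, so it is only a stand-in for HI. The weights, the correlations and the SHI values are assumed.

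Worked line: SHI 0.70 gives d = 0.742 and 0.90 gives d = 1.812. At w = 0.25 and ρ = 0, (0.556 + 0.453)/√(2 × 0.625) = 0.903, and Φ(0.903) = 0.82.

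| SHI alone | w | Apparent SHI AUC, ρ = 0 / 0.3 / 0.6 |
|---|---|---|
| 0.60 | 0.25 | 0.74 / 0.72 / 0.71 |
| 0.60 | 0.50 | 0.86 / 0.83 / 0.80 |
| 0.70 | 0.25 | 0.82 / 0.80 / 0.78 |
| 0.70 | 0.50 | 0.90 / 0.87 / 0.84 |
| 0.95 | 0.25 | 0.98 / 0.96 / 0.95 |
| 0.95 | 0.50 | 0.98 / 0.97 / 0.95 |

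The inflation is large only where SHI is assumed to be much weaker than HI. If SHI is the better mode and the two are correlated, it almost vanishes.

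**5. The same model with SHI read first.** HI (0.90 alone) is now the mode that borrows. With SHI at 0.70 and w = 0.50, HI reads 0.90 / 0.87 / 0.84 at ρ = 0 / 0.3 / 0.6. At w = 0.25 it reads 0.92 / 0.90 / 0.88. With SHI at 0.60, w = 0.50 and ρ = 0.6, it falls to 0.80. So the mode read second can gain or lose.

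**The case against.** The strongest reply is that this is a pilot. Section 7.1 says it is not powered for accuracy, section 7.2 offers only rough estimates, and no aim or endpoint compares SHI with HI. With about 7.5 cases, chance will dominate. That limits the severity. It does not remove the point: accuracy is a primary endpoint, a wide interval does not display bias, and the protection needs no extra reader.

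A second reply is that SHI can never be read alone. Grayscale is part of its display, and the baseline scan comes first. This stands. Putting SHI first among the contrast modes removes carry-over from HI and contrast Doppler only.

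A third is time, since scores for several modes and up to six targeted cores already share the infusion. This stands as a cost.

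Several stronger readings are tempting, and the documents do not support them:

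- *The examiner knew the PSA, the rectal findings or the earlier biopsy sites.* Section 4.1 shows that such information exists, but no section says who the examiner is or what the examiner knows. A demand to withhold it would rest on silence and would restrict information at a clinically indicated biopsy.
- *HI is always seen before SHI.* Section 6.1 lists the modes and does not say that the list is the scanning order. The gap is that no order is set.
- *One physician reads all 50 patients.* The text says only that the examining physician scores each examination.
- *The bias favours SHI throughout.* Steps 3 and 4 show that this fails for specificity, and for AUC when SHI is the better mode.

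**Conclusion.** The gap is real and moderate. One examiner scores every mode live in one session, with no set order and no point at which SHI scores become final. Primary endpoint b can therefore take in HI and contrast Doppler findings. Sensitivity would probably be overstated, in steps of about 13 points per patient; specificity could move either way. How many patients would be affected cannot be calculated from the documents, and the AUC figures only illustrate what assumed weights would do.

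The conclusion assumes that sensitivity and specificity will be computed from the live SHI reading. Section 7.2 does not spell this out, but no other SHI reading is described.

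A reader might infer that putting SHI first makes any SHI advantage over HI conservative. Step 5 shows that it does not, because a weak SHI read first can pull the later HI score down.

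**What to change.** Add to sections 6.1 and 6.2: after the baseline scan, SHI with its paired grayscale image is the first contrast mode swept and scored. Its 12 site scores are entered on the CRF and locked before HI or contrast color Doppler is viewed. The SHI reading is not revised afterwards; correction of recording errors stays under section 9.3. The CRF should record the order in which the modes were viewed, including which mode was on screen while the infusion was adjusted, since section 6.1 does not say.

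Add to section 7.2: SHI accuracy is computed from the locked scores. It is reported as read with knowledge of baseline grayscale and color Doppler and of whatever clinical information the examiner had. HI and contrast Doppler are reported as read after SHI, and any comparison with SHI states that carry-over into them can run in either direction.

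There is a side benefit. Section 1.5 says that Doppler techniques "utilize relatively high energy levels that destroy a large proportion of the microbubbles", so SHI would not follow contrast Doppler. The documents do not show how much this matters during a continuous infusion.

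Cost: protocol wording, a CRF entry, a little time within the 10-12 minutes, and a brief return to SHI for targeting. No extra reader, visit, core or patient is needed. If the order cannot be changed, report the live SHI scores as read with knowledge of all the other modes.

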7.0 STATISTICAL PLAN

7.1 Sample Size Determination

The study is a pilot study, for the purpose of generating preliminary data for a future grant submission. The study is not powered to demonstrate any specific accuracy of CEUS, but rather to accumulate several demonstration cases of SHI in high grade prostate cancer.

Based upon our past experience we expect approximately 30% of our patients to be positive for prostate cancer and half of these (15%) to have a diagnosis of high grade disease. Thus, in a population of 50 patients, the mean expected number of patients with high grade disease would be 7.5. Using an exact binomial probability distribution, the probability of finding at least 5 patients in this sample with high grade disease is 88%. The probability of finding 3 or fewer patients with high grade disease is 4.6%. The probability of not finding a single patient with high grade disease is 0.03%. Thus, the sample size of $n=50$ provides a greater than 95% probability of demonstrating the performance of SHI in at least 3 patients with high grade prostate cancer.

7.2 Statistical Methods

Rough estimates of the sensitivity and specificity of SHI for high grade disease may be obtained if there are sufficient patients with high grade disease. No additional statistical analysis will be performed

7.3 Subject Population(s) for Analysis

All study participants will be included in the analysis.

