THOMAS JEFFERSON UNIVERSITY
Kimmel Cancer Center

Detection of high grade prostate cancer with subharmonic ultrasound imaging, A pilot study.

Principal Investigators:	[name] Department of Radiology Thomas Jefferson University [name] [contact]	[name] Department of Radiology Thomas Jefferson University [name] [contact]
Co-Investigator(s):	[name] Department of Urology [name] Department of Urology [name] Department of Urology	
Funding Sponsor:	NIH R21CA202214	
Regulatory Sponsor:	[name] PhD	
IND Number:	112,241	
Study Product:	Definity	
Protocol Number:	15F.607	

Version:	Date:
1.0	11/2015
1.1	11/2016
1.2	12/01/17

CONFIDENTIAL

This document is confidential and the property of THOMAS JEFFERSON UNIVERSITY. No part of it may be transmitted, reproduced, published, or used by other persons without prior written authorization from the study sponsor.

Study Summary

Title	Detection of high grade prostate cancer with subharmonic ultrasound imaging, A pilot study
Short Title	Using Contrast-enhanced Ultrasound (CE-TRUS) to Identify Aggressive forms of Prostate Cancer
Protocol Number	
Phase	Phase II clinical study – classified as Phase II because the goal is to demonstrate that imaging of the prostate with CEUS is improved with the use of subharmonic imaging
Methodology/Study Design	Pilot cohort study of patients scheduled for prostate biopsy
Study Duration	two years
Study Center(s)	Single-center
Objectives	
 1. To implement SHI technology on a transrectal probe suitable for prostate imaging and biopsy 2. To demonstrate visualization of prostatic vascularity using subharmonic contrast-enhanced imaging. 3. To provide a preliminary estimate of the diagnostic accuracy of contrast-enhanced subharmonic imaging for detection of clinically significant PCa.
Number of Subjects	55 subjects (5 controls and 50 patients)
Diagnosis and Main Inclusion Criteria	
 1. Patients who are scheduled for prostate biopsy 2. and who are able to undergo CEUS
Study Therapy, Dose, Route, Regimen	The study will involve infusion of the ultrasound microbubble contrast agent Definity immediately prior to a prostate biopsy procedure.

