3.0 STUDY DESIGN

3.1 General Design

This study is a pilot phase II clinical trial of 55 patients (5 controls and 50 patients) over the course of 2 years. Experimental software used for subharmonic imaging of other body parts will be adopted to work with the transrectal prostate probe of an FDA approved ultrasound system, specifically the IC5-9D transducer on the Logiq E9 system (GE Healthcare; Milwaukee, WI). In vitro testing will be performed on 5 patients to ensure that the power output of the transducer with the new subharmonic software is within the FDA approved limits for the system power output. After in vitro optimization of the subharmonic mode for imaging, we will conduct a pilot clinical trial of 50 patients over 2 years. All participants will be evaluated with contrast-enhanced transrectal ultrasound (CE-TRUS) prior to prostate biopsy. Subharmonic imaging of the CE-TRUS study will be used to direct targeted biopsy of the prostate with up to 6 biopsy cores. This will be followed by a conventional systematic biopsy of the prostate with 12 cores.

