3.2 Primary Study Endpoints

- a. Demonstration of prostate vascularity with subharmonic contrast-enhanced imaging. Specifically, demonstration of increased prostate vascularity in patients with high risk, aggressive prostate cancer.
- b. Preliminary measures of efficacy (sensitivity and specificity) will be obtained for subharmonic CE-TRUS in the detection of high risk, aggressive prostate cancer after biopsy procedure on 50 patients.

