4.0 SUBJECT SELECTION AND WITHDRAWAL

4.1 Inclusion Criteria

1. Subject must be scheduled for a clinically indicated needle biopsy of the prostate based upon an elevated PSA, abnormal digital rectal examination, or based upon active surveillance of prostate cancer.
2. Subject must be able and willing to give written informed consent for a contrast enhanced ultrasound study of the prostate.
3. Subject must be a male at least 18 years of age when informed consent is obtained.
4. Subject must have a life expectancy that exceeds the duration of the clinical trial.

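### Do the five undefined controls leave the accuracy estimates open between 50 and 55 subjects?

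*Combined protocol and SAP*

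**What the plan says.** The Study Summary gives the number of subjects as "55 subjects (5 controls and 50 patients". Section 3.1 opens in the same way: "This study is a pilot phase II clinical trial of 55 patients (5 controls and 50 patients) over the course of 2 years". It then says "In vitro testing will be performed on 5 patients to ensure that the power output of the transducer" stays within approved limits, and goes on: "After in vitro optimization of the subharmonic mode for imaging, we will conduct a pilot clinical trial of 50 patients over 2 years". It adds that "All participants will be evaluated with contrast-enhanced transrectal ultrasound (CE-TRUS) prior to prostate biopsy".

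Section 3.2b defines the sensitivity and specificity endpoint as obtained "after biopsy procedure on 50 patients". Section 3.2a, on showing prostate vascularity, names no number. Section 4.1 has one set of inclusion criteria, the first being "Subject must be scheduled for a clinically indicated needle biopsy of the prostate". Section 4.4 describes the recruitment of fifty men from the biopsy list, and section 7.1 bases its probabilities on 50 patients.

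Section 4.5.1 keeps the data of anyone whose contrast scan has been done. Section 7.3 states "All study participants will be included in the analysis". Section 7.2 promises no more than rough accuracy estimates, and only if enough patients have high-grade disease.

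**The concern.** The word controls appears only in the two counts of 55. Nothing says who these five are, where they come from, or whether they are scanned or biopsied. The only other mention of five is the in vitro testing sentence in section 3.1, which contradicts itself (bench work is not done on patients) and does not call them controls.

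Each way of reading the five leaves a loose end:

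- **Bench tests.** The count of 55 subjects is then five too high.
- **Men scheduled for biopsy.** Section 4.4 then gives no source for five of them. Sections 4.5.1 and 7.3 would take in their data, while section 3.2b keeps accuracy to 50.
- **Men not scheduled for biopsy.** They fail the first inclusion criterion and do not fit the statement in section 3.1 that everyone is scanned before biopsy.

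At stake would be the denominator of the accuracy estimates, which are a primary endpoint. Two analysts reading sections 3.2b and 7.3 separately could report on different sets of men.

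**Working it through.** **Step 1. Which n does the sample size section use?** The input is section 7.1's high-grade rate of 15%. With X the number of high-grade cases, X ~ Binomial(n, 0.15), the mean is 0.15n and P(X = 0) = 0.85^n. The other two rows are exact binomial tail sums.

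| Quantity | Section 7.1 | n = 50 | n = 55 |
|---|---|---|---|
| Mean | 7.5 | 7.5 | 8.25 |
| P(X ≥ 5) | 88% | 88.8% | 93.0% |
| P(X ≤ 3) | 4.6% | 4.6% | 2.6% |
| P(X = 0) | 0.03% | 0.030% | 0.013% |

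The stated figures are those for n = 50. The section's conclusion, a better than 95% chance of at least three high-grade cases, holds either way: P(X ≥ 3) is 98.6% at 50 and 99.3% at 55.

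**Step 2. Do the sections conflict on the accuracy population?** Section 7.3 is a general rule for the whole study. Section 3.2b is specific to sensitivity and specificity and names 50 biopsied patients. A general statement that everyone is analysed does not put everyone into every estimate. Controls who were scanned could be analysed under section 3.2a, which has no limit of 50, and this satisfies sections 4.5.1 and 7.3 while section 3.2b keeps accuracy at 50. In addition, the Study Summary makes the 12-core biopsy the reference standard, so a man without a biopsy has no place in the two-by-two table.

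**Step 3. What if someone did pool all 55?** The documents give no accuracy values. I assume 7 high-grade cases (near the expected 7.5) with 5 detected, hence 50 − 7 = 43 unaffected patients, and a specificity s between 50% and 80%.

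- Bench tests, or no biopsy: no effect.
- Biopsied men similar to the patients: expected shift zero. The chance that at least one of the five has high-grade disease is 1 − 0.85^5 = 55.6%. One such case takes sensitivity from 5/7 = 71.4% to 5/8 = 62.5% (−8.9 points) or 6/8 = 75.0% (+3.6 points).
- None of the five with high-grade disease, all five negative on subharmonic imaging: the shift is (43s + 5)/48 − s, which is +5.2 points at s = 0.5 and +2.1 at s = 0.8.
- None of the five with high-grade disease, all five positive: the shift is 43s/48 − s, which is −5.2 points at s = 0.5 and −8.3 at s = 0.8. If the five behave like the patients, the last case has probability 0.2^5 = 0.03%.

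For scale, exact (Clopper–Pearson) 95% intervals are 29.0% to 96.3% for 5/7 and 64.0% to 90.0% for 34/43. The shifts are small beside the uncertainty that the design already accepts.

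**The case for a change.** The best argument for acting is that how many people enter a study, and who they are, is basic protocol content, and that this study gives an intravenous agent under an IND. Five subjects have no definition, no recruitment source and no stated role in the analysis, and a few words would settle it. Section 7.3 is the place where an analyst looks for the population, and it does not help.

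Part of this stands. The controls are undefined, section 3.1 calls all 55 patients and then describes a trial of 50, the in vitro sentence is a drafting error, and section 4.4 accounts for only 50 men. Whether 50 or 55 people were to be enrolled cannot be settled from the text.

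The statistical part does not stand. Section 7.3 would gain only a limit that section 3.2b already sets. Writing the figure 50 into it could even do harm. It is a planned number, and the sentence would become false if accrual fell short or a patient had no biopsy result.

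**Conclusion.** No change to the plan follows. The mismatch is real but clerical: five undescribed subjects in two headline counts and one badly worded sentence about bench testing. An analyst who follows section 3.2b obtains accuracy estimates in the biopsied patients, which is the sound population and the one behind section 7.1. No hypothesis test, decision threshold or sample size figure depends on the five.

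The effect is zero if they are bench tests or unbiopsied, and zero in expectation if they are biopsied men like the rest and are pooled against section 3.2b. The single-case shift of −8.9 or +3.6 points in sensitivity, and the extremes of −8.3 to +5.2 points in specificity, rest on my assumed 5/7, 43 unaffected patients and specificity of 50% to 80%. They would matter little in an unpowered pilot that offers only rough estimates. The conclusion rests on reading section 3.2b as the rule for accuracy and section 7.3 as the general rule, which is the natural reading of the two together.
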